5. STATISTICAL METHODS

5.1 GENERAL CONSIDERATIONS

All statistical analyses will be performed using SAS® Version 9.3 (or later) for Windows.

5.1.1 Data Display and Summary

All summaries will be presented by treatment unless specified otherwise. Descriptive statistics including the number of patients, mean, standard deviation (SD), median, minimum, and maximum will be calculated for continuous variables. Frequencies and percentages for each category will be calculated for categorical variables. Percentages will be based on the total number of non-missing values. The number missing will be presented, but without a percentage.

5.1.2 Handling of Missing Values

Unless stated otherwise, missing data will not be imputed.

5.1.3 Statistical Significance and Multiplicity

All hypothesis tests will be two-sided with a 5% significance level, and 95% confidence intervals will be used, unless stated otherwise. No adjustments for multiplicity are planned; p-values will be reported as nominal.

5.1.4 Interim Analysis and Data Monitoring

No interim analyses are planned.

5.1.5 Multicenter Studies

This study is being conducted in approximately 70 centers. Due to the potential of small numbers of patients per center, data will be pooled by center into the following 5 geographic regions (as listed in [Table 5.1-1](#)): Northeast, Southeast, Midwest, Southwest, and West. All analyses using trial center will use this 5-category geographic region variable.

Table 5.1-1. Definition of Geographic Regions

Northeast	Southeast	Midwest	Southwest	West
CT	AL	IA	AZ	CA
DE	AR	IL	NM	CO
MA	FL	IN	OK	ID
MD	GA	KS	TX	MT
ME	KY	MI		NV
NH	LA	MN		OR
NJ	MS	MO		UT
NY	NC	ND		WA
PA	SC	NE		WY
RI	TN	OH		
VT	VA	SD		
	WV	WI		

5.2 ANALYSIS POPULATIONS

5.2.1 Screened Population

The Screened Population consists of all patients who signed informed consent and received a patient identification (PID) number.

5.2.2 Randomized Population

The Randomized Population consists of all patients in the Screened Population who were randomized to a treatment group in the study.

5.2.3 Modified Intent-to-Treat Population

The modified Intent-to-Treat (mITT) Population consists of all patients in the Randomized Population who received at least one dose of study treatment.

5.2.4 Per-Protocol Population

The Per-Protocol (PP) Population consists of all patients in the mITT Population who have a minimum of 6 weeks of eDiary data for the heartburn severity and regurgitation frequency scores and > 80% compliance with study treatment for the available Treatment Period days.

5.2.5 Safety Population

The Safety Population consists of all patients in the Randomized Population who received at least one dose of study treatment.

5.3 PROTOCOL DEVIATIONS

Protocol deviations and Significant Protocol Deviations (SPD) will be identified and documented for all randomized patients prior to unblinding. The number and percentage of subjects with SPDs will be presented by study treatment and SPD category. Listings of protocol deviations and SPDs will also be provided.

5.4 PATIENT DISPOSITION

The number and percentage of patients included in the mITT, PP, and Safety Populations will be presented overall and by treatment group for the Randomized Population. The number of patients in the Screened Population will be presented overall.

The number and percentage of screen failures (i.e., patients who entered the Screening Period but not the Pretreatment Period) and patients ineligible for randomization (i.e., patients who entered the Pretreatment Period but were not randomized), along with the associated reasons for failure or ineligibility, will be tabulated overall for the Screened Population.

The number and percentage of patients who completed treatment, who completed the study, and who prematurely discontinued (overall and by reason for discontinuation) will be presented for each treatment group and overall for the Randomized Population.

5.5 DEMOGRAPHIC AND OTHER BASELINE CHARACTERISTICS

Demographic parameters (age; age group; race; ethnicity; sex; weight; height; and body mass index [BMI], calculated as weight [kg]/(height [m])²) will be summarized by treatment group for the Randomized, mITT, and PP Populations. Baseline efficacy assessments (including GERD symptoms, dyspepsia symptoms, assessments of sleep, bothersomeness assessments, and the degree of relief assessments) will be summarized by treatment group for the mITT and PP Populations.

Abnormalities in patients' medical and surgical histories will be coded using the Medical Dictionary for Regulatory Activities (MedDRA), version 18.1. The number and percentage of patients with abnormalities in medical and surgical histories in each system organ class (SOC) and preferred term (PT) will be summarized by treatment group for the Safety Population.

5.6 MEASUREMENT OF TREATMENT COMPLIANCE

The first dose of study medication will be taken in clinic at the Randomization Visit (Day 1). Patients should take their second dose that evening immediately upon completion of dinner. During the Treatment Period, patients will take study medication BID at home, in the morning (immediately upon completion of breakfast) and in the evening (immediately upon completion of dinner), even on study visit days. The last dose of study medication will be taken the morning of the EOT Visit. The double-dummy dosing requires all patients to take three tablets for each dose.

Dosing compliance for the Treatment Period is defined as the number of tablets taken by a patient during the Treatment Period divided by the number of tablets that were expected to be taken during the Treatment Period multiplied by 100. The total number of tablets taken will be calculated as total number of tablets dispensed minus total number of tablets returned minus total number of tablets lost. The total number of tablets expected to be taken during the Treatment Period is the number of days between the date of first dose taken and the date of last dose taken, inclusive, multiplied by 6 (multiplied by 6 minus 3 if the last dose is a morning dose). Patients will be included in the period summary only for the periods they were on study (i.e., the periods that are prior to or contain the last dose date).

Descriptive statistics for study drug compliance will be presented for the Safety Population by treatment group.

Patients will record their PPI administration each day (once daily) in their eDiary. PPI compliance for a specified period is defined as the number of days for which a patient answered Yes to the PPI administration question in the eDiary divided by the total number of days for which the patient provided an answer (Yes or No) to the PPI administration question in that period multiplied by 100. PPI compliance will be summarized by treatment group for the Safety Population.

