3.6.4 Early Termination Procedures

Patients who discontinue from the study for any reason should complete the assessments required at the EOT Visit (Section 3.6.2.4) at the time of their discontinuation.

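### Compliance is counted only up to the last dose taken, so a patient who stops study drug but stays on study with at least 6 weeks of diary can qualify as Per-Protocol

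*SAP*

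**What the plan says.** SAP 5.2.4 sets two conditions for a treated patient to be Per-Protocol. The patient must "have a minimum of 6 weeks of eDiary data for the heartburn severity and regurgitation frequency scores" and must show "> 80% compliance with study treatment for the available Treatment Period days". Protocol 3.7.1 has the same rule. Neither document defines available days, and neither sets an upper limit on compliance or a minimum time on drug.

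SAP 5.6 supplies the only compliance formula. The denominator is the "number of days between the date of first dose taken and the date of last dose taken, inclusive, multiplied by 6", reduced by 3 when the final dose is a morning one. The numerator is the "total number of tablets dispensed minus total number of tablets returned minus total number of tablets lost". The dosing scheme "requires all patients to take three tablets for each dose", twice a day. For a patient who finishes the course, "The last dose of study medication will be taken the morning of the EOT Visit".

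SAP 7.2 replaces a missing last-dose date with the date of the last eDiary entry. SAP 5.10 runs the efficacy analyses on both the mITT and PP Populations unless otherwise specified. SAP Table 5.10-1 places Week 8, the primary time point, at Days 50-56.

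**The concern.** SAP 5.6 introduces compliance as tablets taken over tablets expected in the Treatment Period, which lasts 8 weeks. It then ends the expected count at the last dose actually taken. Days after a permanent stop drop out of the denominator, so the ratio measures adherence while dosing and says nothing about whether dosing continued.

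This matters for PP because the only other condition is diary data, and a patient can keep a diary without taking tablets. The plan allows for the two to separate. SAP 5.4 counts completion of treatment and completion of the study as different outcomes. Protocol 3.5.1.3 lists discontinuation of treatment as an action taken for an adverse event. Protocol 3.3.2 makes removal for non-compliance discretionary.

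The PP analysis is where a reader would look for the effect in patients who took the drug. If it can hold patients with no exposure in the week that defines the primary parameter, it is a weaker check on the dose contrast.

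The numerator raises a second, smaller issue. A tablet that is neither returned nor entered as lost is treated as swallowed, and the PP rule has a floor of 80% but no review of implausibly high values.

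**Working it through.** **Inputs.** Three tablets per dose, two doses per day, last dose on the morning of the EOT Visit (SAP 5.6). EOT Visit on Day 57 (Protocol 3.3.2). PP threshold above 80% with 6 weeks of diary (SAP 5.2.4). Wallets of 60 tablets (Protocol 3.4.2). The number of wallets dispensed is not stated, so a range is used.

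**Tablets per day and full course.** 3 x 2 = 6 per day, which reproduces the SAP's multiplier. Full course to the morning of Day 57: 57 x 6 - 3 = 339.

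**Early stop, patient stays on study to Day 57.** Assume every dose is taken up to the stop, the rest is returned and the last-dose date is recorded. SAP compliance is 100 x (6 x stop day) / (6 x stop day), which is 100% for any stop day. The share of the full course is 100 x (6 x stop day) / 339.

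| Last full day on drug | Tablets taken | SAP 5.6 compliance | Share of 339 |
|---|---|---|---|
| 20 | 120 | 100% | 35.4% |
| 28 | 168 | 100% | 49.6% |
| 42 | 252 | 100% | 74.3% |
| 45 | 270 | 100% | 79.6% |
| 46 | 276 | 100% | 81.4% |

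Measured against 339, a stop on or before Day 45 falls below the 80% cut. Under SAP 5.6 each of these patients passes it. All of them are off drug throughout Days 50-56.

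**The diary condition.** Six weeks is 42 days. A patient who stops after Day 20 must keep the diary for about 22 more days, and one who stops after Day 28 for about 14 more, to be Per-Protocol. A patient who leaves drug and study together before about Day 42 fails, whatever the compliance score.

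**Missing last-dose date.** For the Day 20 stopper with a last diary entry on Day 57, SAP 7.2 makes the denominator 57 x 6 = 342. Compliance is 120 / 342 = 35.1% and the patient fails. The gap therefore needs a recorded last-dose date.

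**Unaccounted-for tablets.** Assume 6, 7 or 8 wallets dispensed (360, 420 or 480 tablets) and a full-length course. If nothing is returned and nothing is recorded as lost, compliance is 360/339 = 106.2%, 420/339 = 123.9% or 480/339 = 141.6%, whatever was swallowed. If all of it is recorded as lost, compliance is 0%.

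Partial non-return, as (true tablets taken + unused tablets not returned) / 339:

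- 60% adherence (203.4 tablets): 60 unreturned gives 263.4/339 = 77.7%, which fails; 120 unreturned gives 323.4/339 = 95.4%, which passes.
- 70% adherence (237.3 tablets): 60 unreturned gives 297.3/339 = 87.7%, which passes.

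**The case against.** A reader might infer that anyone who quits the drug early becomes Per-Protocol. The documents do not support that. The diary condition stands beside the compliance condition, and no off-drug follow-up is described. Under Protocol 3.6.4, "Patients who discontinue from the study for any reason should complete the assessments required at the EOT Visit" when they discontinue, and those procedures include handing back the diary device. Most patients who leave drug and study together early are therefore removed already. The patient at issue stops tablets but keeps attending and reporting, and nothing in the documents says how common that is.

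A reader might also infer that SAP 5.6 contradicts SAP 5.2.4. Available days is undefined, and SAP 5.6 itself treats being on study as lasting up to the last dose date, so the two can be read together. The problem is what that reading admits.

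Nor do unreturned wallets always inflate the score. The SAP does not say when unreturned tablets become lost tablets. If they are entered as lost, the error reverses and an adherent patient could be excluded. Wallet return is requested at every visit, and accountability is monitored and reconciled.

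Finally, a reader might want PP to exclude patients with poor proton pump inhibitor adherence or prohibited medication. Both documents state the same PP rule without those exclusions, and the SAP summarises these matters by arm. Adding them is a design preference and does not correct an inconsistency.

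What stands on the other side is the limited reach. The trial is described as exploratory, p-values are nominal, and mITT does not depend on compliance.

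**Conclusion.** The point holds in a limited form. With a recorded last-dose date, SAP 5.6 gives full credit to a patient who stops permanently. If that patient stays on study and supplies at least 6 weeks of diary, both PP conditions are met with as little as 35% (stop after Day 20) or 50% (stop after Day 28) of the 339-tablet course. These figures assume perfect dosing before the stop, return of the remainder and attendance to Day 57.

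The inflation from unaccounted-for tablets is also possible under the text. Its size depends on the number of wallets dispensed and on how unreturned tablets are recorded; neither is stated.

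The number of patients affected cannot be derived from the documents. The consequence is confined to the PP analyses and the compliance summary. It would be wrong to infer that the mITT results are at risk. The change is worth making because the rule can place off-drug patients in the PP set and the correction is cheap.

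**What to change.** In SAP 5.2.4 and 5.6, for the PP rule:

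1. Count expected tablets from first dose to the EOT or study-discontinuation visit date (to the morning of the EOT Visit for completers), in place of the last dose taken. The Day 20, 28 and 42 stoppers who stay to Day 57 then score 35.4%, 49.6% and 74.3% and fail the cut.
2. State before unblinding how tablets neither returned nor recorded as lost are classed, and review values above 100% before PP membership is fixed. SAP 5.3 already provides a suitable time for this: "Protocol deviations and Significant Protocol Deviations (SPD) will be identified and documented for all randomized patients prior to unblinding".

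The first change does not alter the score of a patient who leaves drug and study together at about Day 42: with 252 tablets taken and 252 expected, compliance is still about 100%. Whether such a patient belongs in PP is a matter for the 6-week diary floor.

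The cost is SAP wording and derivation code. The tablet counts and dates needed are already collected. The downside is a slightly smaller PP Population.

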5.7 EXTENT OF EXPOSURE

Exposure to study drug for the Safety Population during the double-blind treatment period will be summarized by treatment group in terms of treatment duration, calculated as the number of days from the date of the first dose of double-blind study drug to the date of the last dose of double-blind study drug, inclusive. Treatment duration will also be categorized as <7 days; ≥ 7 days and <14 days; ≥ 14 days and <28 days; ≥ 28 days and <42 days; ≥ 42 days and <56 days; ≥ 56 days.

Patient-years, defined as exposure to the study drug in years, will be summarized by treatment group for the Safety Population.

5.8 PRIOR AND CONCOMITANT MEDICATION

Prior medication is defined as any medication taken before the date of the first dose of double-blind study drug. Concomitant medication is defined as any medication taken on or after the date of the first dose of double-blind study drug during the Treatment Period. Medications started after the date of the last dose of double-blind study drug will not be considered concomitant medications.

Both prior and concomitant medications will be coded by drug name and therapeutic class using World Health Organization Drug Dictionary Enhanced (WHO DDE) December 2015. The use of prior and concomitant medications will be summarized for the Safety Population by the number and percentage of patients in each treatment group receiving each medication within each therapeutic class. If a patient took a specific medication multiple times or took multiple medications in the same category (based on Anatomical-Therapeutic-Chemical classification), that patient would be counted only once for the coded drug name or therapeutic class.

5.9 EDIARY COMPLIANCE

Patients are required to enter their diary assessments into the eDiary before going to bed each night and upon getting up each morning during the Pretreatment and Treatment Periods. A daily report is considered complete if all questions in both the morning diary and evening diary (excluding the weekly assessments) are answered, with the following exceptions.

- For the first day of the Pretreatment Period, only the evening diary is expected.
- For the last day of the Pretreatment Period, only the morning diary is pertinent.
- For the first day of the Treatment Period, only the evening diary is pertinent.
- For the EOT Visit day, only the morning diary is expected.

eDiary compliance will be calculated for baseline (the Pretreatment Period), the Treatment Period, and weekly. For each period, eDiary compliance will be calculated as the number of completed daily reports divided by the expected number of daily reports in the period multiplied by 100. eDiary compliance will be summarized by treatment group for the mITT Population. In addition, the number and percentage of patients with $\geq 80\%$ vs. $<80\%$ eDiary compliance for each period, as well as the number and percentage of patients with ≥ 4 vs. <4 complete daily reports each week, will be presented by treatment group for the mITT Population.

5.10 EFFICACY ANALYSIS

Unless otherwise specified, efficacy analyses will be based on both the mITT and the PP Populations.

Baseline values for efficacy parameters will be derived from the eDiary and/or electronic clinical report form (eCRF) data collected for the last week of the Pretreatment Period (or Week -1), specifically the period from 7 days prior to the day of randomization up to the time of randomization. If data for Week -1 is not available, data for Week -2 (the second last week of the Pretreatment Period) will be used.

For continuous efficacy parameters, the analysis value for an analysis period is defined as the average of the non-missing values during that period.

For weekly responder parameters based on daily eDiary assessments, a patient who missed 4 or more daily assessments during an analysis week will not be considered a responder for that week.

[Table 5.10-1](#) provides the analysis time windows allowed for efficacy analyses based on daily assessments and [Table 5.10-2](#) provides the analysis time windows allowed for efficacy analyses based on weekly assessments.

Table 5.10-1. Analysis Time Windows for Efficacy Analysis – Daily Assessments

Period	Analysis Week	Begins ^a	Ends ^a
Pretreatment (Baseline ^b)	Week -2	Day -14	Day -8
	Week -1	Day -7	Day -1 (Day before randomization) ^c
Treatment	Week 1	Day 1 (Day of Randomization) ^d	Day 7
	Week 2	Day 8	Day 14
	Week 3	Day 15	Day 21
	Week 4	Day 22	Day 28
	Week 5	Day 29	Day 35
	Week 6	Day 36	Day 42
	Week 7	Day 43	Day 49
	Week 8	Day 50	Day 56
	Week 9	Day 57	Day 63
	***	***	***

- a. Relative to the date of randomization (Day 1).
- b. Baseline values for efficacy parameters will be derived from the daily eDiary collected in the Pretreatment Period Week -1 (Week -2 if data from Week -1 not available)
- c. Day 1 for efficacy parameters derived from the morning diary.
- d. Day 2 for efficacy parameters derived from the morning diary.

Table 5.10-2. Analysis Time Windows for Efficacy Analysis – Weekly Assessments

Period	Analysis Week	Begins ^a	Ends ^a
Pretreatment (Baseline ^b)	Week -2	Day -11	Day -5
	Week -1	Day -4	Day -1 (Day before randomization)
Treatment	Week 1	Day 7	Day 10
	Week 2	Day 11	Day 17
	Week 3	Day 18	Day 24
	Week 4	Day 25	Day 31
	Week 5	Day 32	Day 38
	Week 6	Day 39	Day 45
	Week 7	Day 46	Day 52
	Week 8	Day 53	Day 59
	Week 9	Day 60	Day 66

a. Relative to the date of randomization (Day 1).
b. Baseline values for efficacy parameters will be derived from the eDiary collected in the Pretreatment Period Week -1 (Week -2 if data from Week -1 not available)

5.10.1 Primary Efficacy Parameter

The primary efficacy parameter is the percent change from baseline (i.e., the Pretreatment Period) to Week 8 in weekly heartburn severity score (WHSS).

The WHSS for an analysis week is defined as the average of available daily heartburn severity scores (DHSS) during that week. DHSS is defined as the maximum of the 3 items measuring heartburn (Heartburn, Burning feeling behind chestbone or in the center of the upper stomach, and Pain behind chestbone or in the center of the upper stomach) from a particular day collected with the mRESQ-eD instrument. For a handful of patients who were assigned to an older version of the instrument, Burning feeling behind the chestbone and Burning feeling in the center of the upper stomach were assessed separately. For analysis purposes, the maximum of the two will be used to represent the item of Burning feeling behind chestbone or in the center of the upper stomach. Similarly, Pain behind chestbone and Pain in the center of the upper stomach were assessed separately for these patients. For analysis purposes, the maximum of the two will be used.

Percent change from baseline to Week 8 in WHSS (both last-observation-carried-forward [LOCF] and observed-case [OC]) will be summarized by treatment group. Each IW-3718 group will be compared with the placebo group using an analysis of covariance (ANCOVA) model with treatment group and esophagitis status (erosive esophagitis or no erosive esophagitis) as fixed-effect terms and baseline WHSS as a covariate. The least-squares (LS) mean for each treatment group, LSM difference between each IW-3718 group and the placebo group along with the corresponding confidence interval, and p-values for the pairwise comparisons vs. placebo will be presented. In addition, a linear contrast among the LS means for treatment groups will be conducted to test the overall ordinal dose response.

The treatment by esophagitis status interaction will be explored (using an ANCOVA model with an additional term for the interaction and/or plotting treatment group means by esophagitis status) to evaluate whether quantitative or qualitative interaction is present. If warranted, treatment comparisons within each esophagitis status will be conducted.

As a sensitivity analysis, percent change from baseline to Week 8 in WHSS will be evaluated employing a mixed model for repeated measures (MMRM) framework with week (categorical), treatment group, week-by-treatment group, and esophagitis status as fixed-effect terms and baseline WHSS as a covariate. A compound symmetry covariance structure will be used to model the covariance of within-patient results. Exploratory analyses with unstructured and autoregressive (1) covariance structures will also be considered.

The cumulative distribution function (CDF) of percent change from baseline to Week 8 in WHSS will be plotted by treatment group. To aid in the interpretation of the graphical presentation, a two-sample Kolmogorov-Smirnov test will be conducted between each IW-3718 group and the placebo group.

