For the analysis of continuous parameters (e.g., absolute change from baseline and percent change from baseline), descriptive statistics (patient number [n], mean, standard deviation, median, and range) will be presented for each treatment group. Each IW-3718 group will be compared with the placebo group using an analysis of covariance (ANCOVA) model with treatment group, and esophagitis stratum as fixed effect terms and the corresponding baseline efficacy parameter value as a covariate. Least-squares means (LSMs) for each treatment group, a linear contrast among the LSMs to test the overall ordinal dose response, LSMs differences between each IW-3718 group and the placebo group and their corresponding confidence intervals, and p-values for the pairwise comparisons versus placebo will be presented. The treatment by esophagitis stratum interaction term will be explored to evaluate whether quantitative or qualitative interaction(s) are present, and treatment comparisons within each stratum will be conducted, as warranted.

The cumulative distribution function (CDF) of change from baseline for key efficacy parameters will be plotted by treatment group. To aid in the interpretation of the graphical representation of the CDF across treatments, a two-sample Kolmogorov-Smirnov test will be conducted (22). A

p-value ≤ 0.05 indicates that the 2 treatment samples are unlikely to have been drawn from the same continuous distribution by chance alone.

For the analysis of responder parameters (i.e., responder vs. non-responder), the counts and proportion of responders will be calculated for each treatment group. The proportions of responders between each IW-3718 group and the placebo group will be compared using a Cochran-Mantel-Haenszel (CMH) test controlling for esophagitis stratum. The CMH test is the primary analysis for responder parameters. The difference in the proportion of responders between each IW-3718 group and the placebo group as well as the CMH estimates of the odds ratio (IW-3718 over placebo) and the corresponding 95% confidence intervals will also be presented.

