5.10.5 Subgroup Analyses

Subgroup Analyses of efficacy parameters will be based on the mITT Population.

Esophagitis Status

Subgroup analysis by esophagitis status (erosive esophagitis vs. no erosive esophagitis at screening) will be performed for the following efficacy parameters.

- Percent change from baseline to Week 8 in WHSS
- Overall Heartburn Responder
- Percent change from baseline to Week 8 in WRFS
- Overall Regurgitation Responder
- Percent change from baseline to Week 8 in saliva bile acid level

Baseline WHSS

Subgroup analysis by baseline WHSS (≤ 3 vs. >3) will be performed for the following efficacy parameters.

- Percent change from baseline to Week 8 in WHSS
- Overall Heartburn Responder

Baseline WRFS

Subgroup analysis by baseline WRFS (≤ 3 vs. >3) will be performed for the following efficacy parameters.

- Percent change from baseline to Week 8 in WRFS
- Overall Regurgitation Responder

Baseline Bile Acid Level in Saliva

Subgroup analysis by baseline bile acid level in saliva (positive vs. negative) will be performed for the following efficacy parameters.

- Percent change from baseline to Week 8 in WHSS
- Overall Heartburn Responder
- Percent change from baseline to Week 8 in WRFS
- Overall Regurgitation Responder

Bilitec Monitoring Status

Subgroup analysis by Bilitec monitoring status (performed vs. not performed at screening) will be performed for the following efficacy parameters.

- Percent change from baseline to Week 8 in WHSS
- Overall Heartburn Responder
- Percent change from baseline to Week 8 in WRFS
- Overall Regurgitation Responder

Bilitec Bile Acid Status

Subgroup analysis by Bilitec bile acid status (positive vs. negative at screening) will be performed for the following efficacy parameters.

- Percent change from baseline to Week 8 in WHSS
- Percent change from baseline to Week 8 in WRFS

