5.13 DETERMINATION OF SAMPLE SIZE

The sample size per arm was determined by estimating the overall power of a linear trend test in a one-way design that included placebo and all the active treatment arms (500 mg BID, 1000 mg BID, and 1500 mg BID of IW-3718). The efficacy endpoint of interest in the previous Phase 2a study (ICP-3718-201) was change from baseline in daytime heartburn defined as the presence of heartburn since the patient awoke that morning (assessed in the evening) and assessed with an 11-point [0 to 10] NRS, where 0=none and 10=very severe. In that study, IW-3718 demonstrated treatment differences near 0.70 points for change over the treatment period (e.g., -0.73 vs. -1.38 for placebo and IW-3718, respectively), and standard deviations near 1.35 for the LSMS.

Employing these historical values, a study with 58 patients per arm (the expected number of patients at Week 8 given an enrollment of 260 patients) will have statistical power of at least 80% for the overall trend test (i.e., linear contrast) where the highest active treatment arm reflects 110% of the previously observed treatment difference and the lowest 2 active treatment arms reflect 55% of the same (two-sided, $\alpha=0.05$). At the proposed sample size, a subsequent pairwise comparison between placebo and an active treatment arm reflecting the previously observed treatment difference will have 80% statistical power (two-sided, $\alpha=0.05$).

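### The sensitivity MMRM for the primary parameter is set at compound symmetry, which can misstate the Week 8 standard error in either direction; an unstructured covariance with a fallback order is a cheap improvement

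*SAP*

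**What the plan says.** SAP 5.10.1 defines the primary parameter as percent change in WHSS from baseline to Week 8 and begins the analysis with: "Percent change from baseline to Week 8 in WHSS (both last-observation-carried-forward [LOCF] and observed-case [OC]) will be summarized by treatment group". An ANCOVA with treatment group, esophagitis status and baseline WHSS follows. It gives the pairwise comparisons with placebo, and then: "In addition, a linear contrast among the LS means for treatment groups will be conducted to test the overall ordinal dose response".

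The next paragraph adds an MMRM as a sensitivity analysis. Its fixed effects are week, treatment group, their interaction and esophagitis status, with baseline WHSS as a covariate. There is no week-by-baseline term, so one baseline slope serves all weeks. The within-patient covariance is set at compound symmetry. Unstructured and AR(1) structures are named only as exploratory analyses that the sponsor will consider. No rule says which of these results counts if they differ. The protocol (3.7.4.1) specifies the ANCOVA and has no MMRM.

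**The concern.** A sensitivity analysis is useful only if its own standard error can be trusted. Compound symmetry assumes one variance at every week and one correlation between any two weeks. The quantity of interest is at Week 8 alone. If the residual variance at Week 8 differs from the average over the eight weeks, the model still uses the pooled figure. When Week 8 is more variable than average, the MMRM looks more supportive of the ANCOVA than it should. When Week 8 is less variable, it looks less supportive.

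Equal variances should not be taken for granted. If the correlation with baseline fades over the weeks, a single baseline slope leaves unequal residual variances even when the raw variances are equal. Of the two alternatives the SAP mentions, AR(1) in its usual form also assumes equal variances. Only the unstructured option addresses the problem, and it is not committed to.

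**Working it through.** **1. The plan's own figures.** Inputs from SAP 5.13: 58 per arm, difference 0.70, SD 1.35, two-sided 0.05, arm effects 0, 55%, 55% and 110% of 0.70 (0, 0.385, 0.385, 0.77).
- Trend, contrast (-3, -1, 1, 3): the contrast value is -0.385 + 0.385 + 3 × 0.77 = 2.31. Its SE is 1.35 × sqrt(20/58) = 0.793. The noncentrality is 2.914 and power is 82.7% (t, 228 df).
- Pairwise: 0.70 / (1.35 × sqrt(2/58)) = 2.79. Power is 79.1% (114 df) to 79.4% (228 df).

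Both agree with the stated 80%. They concern the main comparison, and nothing below changes them.

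**2. Compound symmetry with complete data.** With a mean for every week and arm, the fitted common variance is the average of the weekly residual variances. For the Week 8 contrast:

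model SE / true SE = sqrt(mean weekly variance / Week 8 variance)

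type I error = 2 × Φ(-1.96 × ratio)

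Assumption: the SD moves linearly from Week 1 (set to 1) to Week 8.

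| Week 8/Week 1 variance | Mean variance | SE ratio | Type I error |
|---|---|---|---|
| 1.5 | 1.243 | sqrt(1.243/1.5) = 0.910 | 7.4% |
| 1.0 | 1.000 | 1.000 | 5.0% |
| 0.667 | 0.829 | sqrt(0.829/0.667) = 1.115 | 2.9% |

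With the loss implied by SAP 5.13 (1 - 58/65 = 10.8%) and an assumed within-patient correlation (stable patient share 0.5, AR(1) 0.8 for the rest), the ratios become 0.896, 0.987 and 1.101, and the type I errors 7.9%, 5.3% and 3.1%. Unequal variance is the main driver.

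**3. Can the model itself create unequal variances?** Assume equal raw variances (set to 1) and a correlation with baseline at week k of r(k) = s + (1 - s) × a^k, where s is the stable patient share and a the AR(1) parameter. With complete data the single fitted slope b is the mean of r(k) over the eight weeks. The residual variance at week k is 1 + b² - 2 × b × r(k), and its average over weeks is 1 - b².
- s = 0.3, a = 0.3: b = 0.337 and r(8) = 0.300. Average 0.886, Week 8 0.911. Ratio sqrt(0.886/0.911) = 0.986, type I error 5.3%.
- s = 0.7, a = 0.8: b = 0.825 and r(8) = 0.750. Average 0.320, Week 8 0.443. Ratio sqrt(0.320/0.443) = 0.850, type I error 9.6%.

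Over s from 0.3 to 0.7 and a from 0.3 to 0.8, the SE is 1% to 15% too small. This uses the change scale as an approximation to percent change.

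**4. Direct check by simulation.** Week 8 trend under the null, 260 patients, complete data, 4000 replicates (Monte Carlo SE 0.3 to 0.5 points):

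| s / a | Compound symmetry | Unstructured |
|---|---|---|
| 0.3 / 0.6 | 5.8% | 4.4% |
| 0.5 / 0.8 | 8.7% | 4.8% |
| 0.7 / 0.8 | 10.1% | 5.7% |

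**The case against.** The strongest reply has three parts.

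First, this is a labelled sensitivity analysis in a trial the protocol (3.7.2) calls exploratory, and unstructured and AR(1) fits are already mentioned. The first half stands and limits the point. The second helps less: those fits are optional, and AR(1) shares the equal-variance assumption.

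Second, the direction is unknown. This stands. The 9.6% end of the range needs an assumed baseline-to-Week 1 correlation of 0.7 + 0.3 × 0.8 = 0.94, which is high. Floor effects on the percent-change scale can also push the other way. With scores limited to 0-5, baseline at least 2 and an assumed mean fall of 2.0 points by Week 8, the SE was too large (ratio 1.03 to 1.07) in four of six correlation cases. With smaller falls it was mostly too small. It would be wrong to infer that compound symmetry always favors the drug.

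Third, a reader might go further and infer an inflated error rate for the primary result, because the SAP does not rank LOCF against observed cases or mITT against PP. It says "Unless otherwise specified, efficacy analyses will be based on both the mITT and the PP Populations", restricts only other analyses ("Subgroup Analyses of efficacy parameters will be based on the mITT Population"), and its default ("Unless stated otherwise, missing data will not be imputed") does not settle the matter because 5.10.1 brings LOCF in. If any of the four trend results could be claimed, simulation under assumed dropout and non-compliance gives 7.4% to 8.9%. The documents do not support that reading. P-values are declared nominal (SAP 5.1.3), and no rule lets success rest on whichever version is significant.

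The order of tests is not a defect of substance either. The protocol lists "a linear contrast among the LSMs to test the overall ordinal dose response, LSMs differences between each IW-3718 group and the placebo group", and SAP 5.13 speaks of "a subsequent pairwise comparison between placebo and an active treatment arm", so trend first is already implied. With nominal p-values, sentence order changes no estimate.

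**Conclusion.** The point holds for the sensitivity MMRM only. Fixing compound symmetry makes the Week 8 standard error depend on an equal-variance assumption that the documents give no data to support. Under plausible but assumed variance ratios of 1.5 and 0.667, the error runs from 9% too small to 11% too large. The single baseline slope alone could make it 1% to 15% too small. All these figures rest on assumed variances and correlations.

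The ANCOVA, its trend contrast and its stated power are untouched, and no stated error rate is breached. The missing ranking of LOCF against observed cases, and of mITT against PP, is a matter of clarity.

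It would also go too far to require observed cases because the sample size counts "the expected number of patients at Week 8 given an enrollment of 260 patients". A head count is not a missing-data argument. In a null check with assumed inputs, the observed-case trend test rejected in 5.3% of trials under random dropout. It rejected in 11.8% when an equal 10.8% loss was outcome-related on placebo only (correlation 0.7), and in 10.3% when outcome-related loss (correlation 0.5) rose with dose from 5% to 18%.

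**What to change.** Before unblinding, replace the two covariance sentences in SAP 5.10.1 with:

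> The MMRM will use an unstructured covariance with Kenward-Roger degrees of freedom. If it does not converge, heterogeneous Toeplitz and then heterogeneous compound symmetry will be used, in that order. Compound symmetry results are supportive only.

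Both fallbacks keep a separate variance for each week, which is the property that matters here.

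The cost is a short SAP edit. The data, software, sample size and main model stay as they are, and no protocol change is needed. The downside is 8 × 9 / 2 = 36 covariance parameters with about 260 patients and possible non-convergence, which the fallback order covers.

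As a minor clarification, the sponsor may also state which missing-data rule and which population lead for the primary parameter, with the reason. No particular choice is prescribed.
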